### 7.3 LOST TO FOLLOW-UP

A participant will be considered lost to follow-up if he or she fails to return for the day 28 visit and is unable to be contacted by the study site staff. A participant will be considered “at-risk” to be lost to follow-up if he or she is unable to be contacted by the study site staff during the safety assessment period between the date of vaccine dose administration and the day 28 follow up visit.

The following actions must be taken if a participant fails to return to the clinic for a required study visit or cannot be reached for protocol-specified remote safety assessments:

- The site will attempt to contact the participant and reschedule the missed calls/visit and counsel the participant on the importance of maintaining the assigned visit schedule and ascertain if the participant wishes to and/or should continue in the study.

- Before a participant is deemed lost to follow-up, the investigator or designee will make every effort to regain contact with the participant (where possible, 3 telephone calls and, if necessary, a certified letter to the participant's last known mailing address or local equivalent methods). These contact attempts should be documented in the participant's medical record or study file.
- Should the participant continue to be unreachable, he or she will be considered to have withdrawn from the study with a primary reason of lost to follow-up.

## 8 STUDY ASSESSMENTS AND PROCEDURES

### 8.1 EFFICACY ASSESSMENTS

**Please refer to the Study Calendar (Section 1.3) for a complete list of protocol-related assessments.**

A blood specimen collection will be performed on day 28 (+/- 3 days) after the administration of the booster dose of the Moderna mRNA COVID-19 vaccine. An anti-SARS-CoV2 IgG Ab titer will be measured using this sample. This is the primary efficacy assessment being performed as part of this trial.

### 8.2 SAFETY AND OTHER ASSESSMENTS

Safety Assessments: participants will have a medical history, vitals, and physical exam and bloodwork for laboratory testing including cardiac biomarkers performed during screening and on day 28 (+/- 3 days). Participants will also be contacted by phone/text/email/video platform on days 2-8, 15, and 22 to document any AEs experienced. Any patients reporting chest pain, palpitations, shortness of breath, or other symptoms which in the opinion of the treating physician suggest cardiac etiology will be asked to have additional bloodwork done to measure cardiac biomarkers (hsTrop I, BNP).

**Baseline Patient characteristics:** The patient's chart in the EMR will be accessed to document general demographics, their hematologic diagnosis and the status of that disease, current and past treatment history for the underlying hematologic condition, other past medical history, medications, and baseline laboratory parameters (including but not limited to neutrophil count, lymphocyte count, immunoglobulin levels). These and other variables (TBD) will be entered into a CRF to be used for eventual univariate and multivariate analyses. Health Insurance Portability and Accountability Act (HIPAA) rules, other relevant federal or state laws, and local institutional requirements will be followed, as applicable.

Blood sample collection for future correlative testing (e.g., immune cell profiling, assessment of immune exhaustion, etc). The following samples will be collected and stored in [name]'s laboratory: **one 15 mL EDTA tube of peripheral blood** obtained prior to administration of the booster dose, and **a second 15 mL EDTA tube of peripheral blood obtained at the day 28 visit**. The first correlative testing we are planning to perform is a detailed anti-viral protein antibody evaluation using the Bio-Plex Pro SARS-CoV-2 Serology assay. This assay is a sensitive and specific method to monitor the antibody immune response profile against viral proteins. There are three isotype-specific 4-plex panels that measure antibodies against SARS-CoV-2 Nucleocapsid, Receptor Binding Domain, Spike 1, and Spike 2 viral proteins. The isotype-specific antibodies detected are IgA, IgG, and IgM. The viral-protein-coated beads can be used to assay antibodies in multiple species and only need to be paired with a species-specific biotinylated

antibody for detection. The results will elucidate the spectrum of humoral response over time before and after COVID-19 vaccine booster administration or natural exposure to SARS-CoV-2 compared to those obtained using the CLIA-certified assay currently in clinical use. Further, it will provide useful information regarding any additional humoral response to vaccination amongst patients who have not only been previously vaccinated but also had a prior COVID-19 infection. Additional correlative testing may be performed with internal and/or external partners such as Adaptive Biosciences with the intention of characterizing other aspects of patients' immune status through T-Cell profiling, including analysis of T-cell receptor (TCR) reactivity against COVID-19 antigens. Any such research will always involve de-identified samples and patient's privacy will be protected.

## 8.3 ADVERSE EVENTS AND SERIOUS ADVERSE EVENTS

### 8.3.1 DEFINITION OF ADVERSE EVENTS (AE)

Adverse event means any untoward medical occurrence associated with the use of an intervention in humans, whether or not considered intervention-related (21 CFR 312.32 (a)).

### 8.3.2 DEFINITION OF SERIOUS ADVERSE EVENTS (SAE)

An adverse event (AE) or suspected adverse reaction is considered "serious" if, in the view of either the investigator or sponsor, it results in any of the following outcomes: death, a life-threatening adverse event, inpatient hospitalization or prolongation of existing hospitalization, a persistent or significant incapacity or substantial disruption of the ability to conduct normal life functions, or a congenital anomaly/birth defect. Important medical events that may not result in death, be life-threatening, or require hospitalization may be considered serious when, based upon appropriate medical judgment, they may jeopardize the participant and may require medical or surgical intervention to prevent one of the outcomes listed in this definition. Examples of such medical events include allergic bronchospasm requiring intensive treatment in an emergency room or at home, blood dyscrasias or convulsions that do not result in inpatient hospitalization, or the development of drug dependency or drug abuse.

### 8.3.3 CLASSIFICATION OF AN ADVERSE EVENT

#### 8.3.3.1 SEVERITY OF EVENT

AEs will be graded according to CTCAE v4 criteria.

For adverse events (AEs) not included in the CTCAE grading system, the following guidelines will be used to describe severity.

- **Mild** – Events require minimal or no treatment and do not interfere with the participant's daily activities.
- **Moderate** – Events result in a low level of inconvenience or concern with the therapeutic measures. Moderate events may cause some interference with functioning.

- **Severe** – Events interrupt a participant’s usual daily activity and may require systemic drug therapy or other treatment. Severe events are usually potentially life-threatening or incapacitating. Of note, the term “severe” does not necessarily equate to “serious”.

#### 8.3.3.2 RELATIONSHIP TO STUDY INTERVENTION

All adverse events (AEs) must have their relationship to study intervention assessed by the clinician who examines and evaluates the participant based on temporal relationship and his/her clinical judgment. The degree of certainty about causality will be graded using the categories below. In a clinical trial, the study product must always be suspect.

- **Definitely Related** – There is clear evidence to suggest a causal relationship, and other possible contributing factors can be ruled out. The clinical event, including an abnormal laboratory test result, occurs in a plausible time relationship to study intervention administration and cannot be explained by concurrent disease or other drugs or chemicals.
- **Probably Related** – There is evidence to suggest a causal relationship, and the influence of other factors is unlikely. The clinical event, including an abnormal laboratory test result, occurs within a reasonable time after administration of the study intervention, is unlikely to be attributed to concurrent disease or other drugs or chemicals.
- **Potentially Related** – There is some evidence to suggest a causal relationship (e.g., the event occurred within a reasonable time after administration of the trial medication). However, other factors may have contributed to the event (e.g., the participant’s clinical condition, other concomitant events). Although an AE may rate only as “possibly related” soon after discovery, it can be flagged as requiring more information and later be upgraded to “probably related” or “definitely related”, as appropriate.
- **Unlikely to be related** – A clinical event, including an abnormal laboratory test result, whose temporal relationship to study intervention administration makes a causal relationship improbable (e.g., the event did not occur within a reasonable time after administration of the study intervention) and in which other drugs or chemicals or underlying disease provides plausible explanations (e.g., the participant’s clinical condition, other concomitant treatments).
- **Not Related** – The AE is completely independent of study intervention administration, and/or evidence exists that the event is definitely related to another etiology. There must be an alternative, definitive etiology documented by the clinician.

#### 8.3.3.3 EXPECTEDNESS

The Principal Investigator or treating Co-Investigator will be responsible for determining whether an adverse event (AE) is expected or unexpected. An AE will be considered unexpected if the nature, severity, or frequency of the event is not consistent with the risk information previously described for the study intervention.

#### 8.3.4 TIME PERIOD AND FREQUENCY FOR EVENT ASSESSMENT AND FOLLOW-UP

The occurrence of an adverse event (AE) or serious adverse event (SAE) may come to the attention of study personnel during study visits and interviews of a study participant presenting for medical care, or upon review by a study monitor.

All AEs including local and systemic reactions not meeting the criteria for SAEs will be captured on the appropriate case report form (CRF). Information to be collected includes event description, time of onset, clinician's assessment of severity, relationship to study product (assessed only by those with the training and authority to make a diagnosis), and time of resolution/stabilization of the event. All AEs occurring while on study must be documented appropriately regardless of relationship. All AEs will be followed to adequate resolution.

Any medical condition that is present at the time that the participant is screened will be considered as baseline and not reported as an AE. However, if the study participant's condition deteriorates at any time during the study, it will be recorded as an AE.

Changes in the severity of an AE will be documented to allow an assessment of the duration of the event at each level of severity to be performed. AEs characterized as intermittent require documentation of onset and duration of each episode.

All reportable events with start dates occurring any time after informed consent is obtained until 7 (for non-serious AEs) or 30 days (for SAEs) after the last day of study participation will be recorded in the participant's study chart. At each study visit, the investigator will inquire about the occurrence of AE/SAEs since the last visit. Events will be followed for outcome information until resolution or stabilization.

---

### 8.3.5 ADVERSE EVENT REPORTING

AE reporting to the IRB and/or Karmanos Data Safety and Monitoring Committee will be carried out according the Karmanos Cancer Institute SOP.

---

### 8.3.6 SERIOUS ADVERSE EVENT REPORTING

The study clinician will immediately report any serious adverse event, whether or not considered study intervention related, including those listed in the protocol or investigator brochure and must include an assessment of whether there is a reasonable possibility that the study intervention caused the event. Study endpoints that are serious adverse events (e.g., all-cause mortality) must be reported in accordance with the protocol unless the event is unexpected and there is evidence suggesting a causal relationship between the study intervention and the event (e.g., death from anaphylaxis). In that case, the investigator must immediately report the event to the DSMC and IRB.

SAEs and any vaccine administration errors for protocol 2021-036 will be reviewed at the Myeloma and Amyloidosis biweekly research team meeting and any reportable events will be reported to the Vaccine Adverse Event Reporting System (VAERS) and Moderna TX, Inc.

All serious adverse events (SAEs) will be followed until satisfactory resolution or until the site investigator deems the event to be chronic or the participant is stable. Other supporting documentation of the event requested by the IRB or DSMC should be provided as soon as possible.

The study sponsor will be responsible for notifying the Food and Drug Administration (FDA) of any unexpected fatal or life-threatening suspected adverse reaction as soon as possible, but in no case later than 7 calendar days after the sponsor's initial receipt of the information.

#### 8.3.7 REPORTING EVENTS TO PARTICIPANTS

All participants will be informed of AEs or SAEs occurring during the conduct of this trial which in the opinion of the PI change the risk/benefit profile of the intervention and/or which may impact participants' willingness to continue on the protocol. Such information will be conveyed to participants by phone, email, and/or certified letter to ensure their awareness.

#### 8.3.8 EVENTS OF SPECIAL INTEREST

None (Not applicable)

#### 8.3.9 REPORTING OF PREGNANCY

The CDC recommends that pregnant or breastfeeding women be vaccinated against COVID-19. Neither pregnancy nor breastfeeding is an exclusion to participating in this trial. Any participant who is pregnant at the time of enrollment or becomes pregnant during the course of participation in the trial will be asked to inform her treating physician of the pregnancy so that information regarding CDC and FDA monitoring programs related to this can be provided.

### 8.4 UNANTICIPATED PROBLEMS

#### 8.4.1 DEFINITION OF UNANTICIPATED PROBLEMS (UP)

The Office for Human Research Protections (OHRP) considers unanticipated problems involving risks to participants or others to include, in general, any incident, experience, or outcome that meets all of the following criteria:

- Unexpected in terms of nature, severity, or frequency given (a) the research procedures that are described in the protocol-related documents, such as the Institutional Review Board (IRB)-approved research protocol and informed consent document; and (b) the characteristics of the participant population being studied;
- Related or possibly related to participation in the research ("possibly related" means there is a reasonable possibility that the incident, experience, or outcome may have been caused by the procedures involved in the research); and
- Suggests that the research places participants or others at a greater risk of harm (including physical, psychological, economic, or social harm) than was previously known or recognized.

#### 8.4.2 UNANTICIPATED PROBLEM REPORTING

[The investigator will report unanticipated problems (UPs) to the reviewing Institutional Review Board (IRB). The UP report will include the following information:

- Protocol identifying information: protocol title and number, PI's name, and the IRB project number;
- A detailed description of the event, incident, experience, or outcome;
- An explanation of the basis for determining that the event, incident, experience, or outcome represents an UP;
- A description of any changes to the protocol or other corrective actions that have been taken or are proposed in response to the UP.

To satisfy the requirement for prompt reporting, UPs will be reported using the following timeline:

- UPs that are serious adverse events (SAEs) will be reported within 24 hours of the investigator becoming aware of the event.
- Any other UP will be reported to the IRB and to the DCC/study sponsor within 72 hours of the investigator becoming aware of the problem.
- All UPs should be reported to appropriate institutional officials and the Office for Human Research Protections (OHRP) according to KCI/WSU institutional requirements.

#### 8.4.3 REPORTING UNANTICIPATED PROBLEMS TO PARTICIPANTS

All participants will be informed of UPs occurring during the conduct of this trial which in the opinion of the PI change the risk/benefit profile of the intervention and/or which may impact participants' willingness to continue on the protocol. Such information will be conveyed to participants by phone, email, and/or certified letter to ensure their awareness.

### 9 STATISTICAL CONSIDERATIONS

#### 9.1 OBJECTIVES

##### 9.1.1 PRIMARY OBJECTIVE

To determine whether booster dosing with the Moderna COVID-19 vaccine can induce humoral immune responses in patients with hematologic malignancies who did not have an adequate response to prior first vaccination with any of the SARS-CoV2 vaccines authorized for use in the USA.

##### 9.1.2 SECONDARY OBJECTIVES

1. To determine whether booster dosing with the Moderna COVID-19 vaccine is safe in patients with multiple myeloma, AL amyloidosis, or other hematologic malignancies.
2. To compare the humoral immune responses between the patients who had a WEAK POSITIVE RESPONSE to prior vaccine (Cohort 3) vs. those with NO RESPONSE to prior vaccination (Cohorts 1 and 2).

3. To descriptively summarize clinical and immune characteristics which contribute to likelihood of responding to booster dosing with the Moderna COVID-19 vaccine.

## 9.2 END POINTS

The primary and second secondary endpoints are the observed response rate of anti-SARS-CoV2 IgG antibody seroconversion (positive vs. negative) measured 28 days (+/- 3 days) following a booster dose of the Moderna mRNA COVID-19 vaccine.

The first secondary endpoints are AEs and SAEs observed in participants, determined according to daily phone calls or video chats. The third secondary endpoints are (a) clinical characteristics of enrolled participants, including treatment history, disease, status, or presence of immunoparesis (i.e., hypogammaglobulinemia) and (b) characterization of patients' immune status through lymphocyte subset profiling, cytokine level analysis, and assessment of immune exhaustion markers.

## 9.3 SAMPLE SIZE DETERMINATION

The specific hypothesis being tested is that it may be possible to induce a protective humoral immune response with a booster dose of the Moderna COVID-19 vaccine in patients with hematologic malignancies who did not have an adequate response to first vaccination with any of the available COVID-19 vaccines. The null hypothesis is that 5% or less of patients who have an anti-SARS-CoV2-IgG Ab titer of less than 2.0 S/CO will spontaneously develop a higher titer. We hypothesize that at least 15% of patients in each cohort will develop a titer of 2.0 S/CO or greater in response to the vaccine, without toxicity in excess of that previously described amongst COVID-19 vaccine recipients.

Thus, the sample size for each cohort of this trial was determined using the Phase 2 single-arm single-stage design based on the following statistical assumptions:  $p_0=5\%$ ,  $p_1=15\%$ , 1-sided alpha = 5%, and power = 80%. In this case, 52 patients would be enrolled to each of the three cohorts. In each cohort, at least 6 patients would need to develop an anti-SARS-CoV2-IgG Ab titer of  $>2.0$  S/CO to reject the null hypothesis. Therefore, a total of 156 response-evaluable patients would be enrolled in this 3-parallel cohort, single-arm, single-stage Phase 2 trial. Given that the study intervention is a single vaccination, and the primary endpoint requires a single visit for a physical a blood sample collection, there should be relatively few non-evaluable patients. Patients who are non-evaluable for the primary endpoint will be replaced only if it becomes evident that this is needed to determine whether or not the primary endpoint is met in any/all of the cohort(s). We expect this will amount to no more than 5 additional patients in any of the three cohorts, so the maximum number of enrolled participants is 171 (= 57 x 3 cohorts).

The size of the trial will also permit a comparison of the likelihood of developing a strong positive response amongst the pooled participants form Cohorts 1 and 2 (i.e., the participants with NO RESPONSE to prior vaccination) versus the participants in Cohort 3 (i.e., the patients who had a WEAK POSITIVE RESPONSE to prior vaccine) as the second secondary objective. We hypothesize that the absolute difference in response rate between Cohort 3 vs. Cohort 1+2 is 20% or more against the response rate of 15% in Cohort 1+2 (i.e., Cohort 3: 35% vs. Cohort 1+2: 15%). The sample sizes of 156

(Cohort 3: 52 vs. Cohort 1+2: 104) will achieve 82.7% power to detect a difference of 20% between two groups at a 1-sided 5% level when the Fisher's exact test is used.

Each cohort in the primary object will be tested at a 1-sided 5% level and the second secondary objective will be also evaluated at a 1-sided 5% level. No correction for multiple comparison is planned between these primary and second secondary objectives

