### 5 STUDY POPULATION

#### 5.1 INCLUSION CRITERIA

In order to be eligible to participate in this study, an individual must meet all of the following criteria:

1. Provision of signed and dated informed consent form
2. Stated willingness to comply with all study procedures and availability for the duration of the study
3. Male or female, aged 18 years of age or older
4. Previously diagnosed with MM/AL amyloidosis (Cohorts 1 or 3) or other hematologic malignancy (Cohorts 2 or 3).
5. Previously received any one of the available COVID-19 vaccines (between 4 and 36 weeks prior to enrollment)
6. Anti-SARS-CoV2 IgG antibody titer of results less than 1.0 units (Cohorts 1 and 2), or 1.0-1.99 units (Cohort 3). Antibody titers will be measured within 14 days of enrollment.
7. If currently receiving potentially immunosuppressive anti-neoplastic therapy for their underlying hematologic condition, a two-week interruption in therapy before and after the booster dose of vaccine is ENCOURAGED BUT NOT REQUIRED (physician discretion).

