## 9.4 ANALYSIS PLAN

### 9.4.1 EFFICACY ANALYSES

Within each cohort, all participants who receive the protocol-specified booster dose of the Moderna COVID-19 vaccine and then have blood sampled within the protocol-specified time window will be included in the efficacy analysis ("efficacy analysis datasets"). There will be an efficacy dataset for each cohort individually.

For the primary and second secondary objectives, the response rate (RR), which is the primary endpoint, will be summarized with frequency, percentage and its associated 2-sided 90% confidence interval (i.e., 1-sided 95% confidence interval), separately by each cohort and by the combined cohort (Cohort 1+2).

For the second secondary objectives, the Fisher's exact test will be used to compare between Cohort 3 vs. Cohort 1+2.

For the third secondary objective, the patient demographic, clinical, and immune characteristics will be summarized by mean, median, standard deviation, range, confidence interval for continuous variables and by frequency, percentage and its associated confidence interval for categorical variables.

As an exploratory analysis, univariable logistic models will be used to explore the associations between patient characteristics and the treatment response.

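### Response is a single Day-28 reading at 2.0 S/CO with no required rise, and Cohort 3 starts just below that level: add a fold-rise sensitivity analysis and state the cut-off one way

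*Combined protocol and SAP*

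**What the plan says.** Section 5.1 assigns patients to cohorts by baseline titre: "less than 1.0 units (Cohorts 1 and 2), or 1.0-1.99 units (Cohort 3"). Section 4.1 gives the same ranges in S/CO. The study calendar (1.3) lists one titre at screening and one at Day 28.

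Section 9.3 is the only place that puts a number on response. The null is common to all cohorts: "The null hypothesis is that 5% or less of patients who have an anti-SARS-CoV2-IgG Ab titer of less than 2.0 S/CO" will rise spontaneously. The alternative is also common: "We hypothesize that at least 15% of patients in each cohort will develop a titer of 2.0 S/CO or greater". The design uses "1-sided alpha = 5%, and power = 80"%, so that "52 patients would be enrolled to each of the three cohorts". The decision rule reads "In each cohort, at least 6 patients would need to develop an anti-SARS-CoV2-IgG Ab titer of" more than 2.0 S/CO. That is a strict inequality, whereas the hypothesis just before it includes 2.0 itself.

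For objective 2, section 9.3 assumes 35% in Cohort 3 against 15% in Cohorts 1 and 2 pooled (52 versus 104 patients) and states 82.7% power. Section 9.4.1 says that "the Fisher's exact test will be used to compare between Cohort 3 vs. Cohort 1+2".

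No section sets a minimum rise, a confirmatory repeat test, an assay precision figure or a baseline-adjusted comparison. The synopsis endpoints and the primary endpoint in section 3 describe seroconversion from negative to positive, and section 9.2 contrasts positive with negative. None of these mentions 2.0 S/CO.

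**The concern.** A patient who moves from 1.95 to 2.02 S/CO counts as a responder, although assay variation alone could produce that change. Only Cohort 3 lies directly under the cut-off, yet its null rate is the one used for patients who start far below it. Two conclusions are exposed. Cohort 3 could meet its 6-of-52 rule partly through crossings that owe nothing to the booster. And a significant objective 2 result could reflect where the two groups started rather than how they reacted to vaccination.

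**Working it through.** **The plan's own figures.** Inputs from 9.3: n = 52, success at 6 or more, p0 = 5%, p1 = 15%. Exact binomial: P(X ≥ 6 | 52, 0.05) = 4.45% and P(X ≥ 6 | 52, 0.15) = 81.2%. Fifty-two is the smallest n that meets both limits. Exact enumeration of the 1-sided Fisher test at 35% versus 15%, 52 versus 104, gives 83.3% power, close to the stated 82.7%. The arithmetic is sound; the question is what counts as a response.

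**Rise needed to reach 2.0**, as 2.0/baseline − 1:

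- from 1.99: 0.5%
- from 1.98: 1.0%
- from 1.00: 100%
- from 0.99: 102%
- from 0.50: 300%

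**Crossing with no true change.** The CV is assumed, since the documents give none. Log-normal error has SD σ = √ln(1 + CV²) on the log scale. If both readings carry error, a patient whose screening reading is x reads 2.0 or more at Day 28 with probability 1 − Φ[ln(2/x)/(√2·σ)], taking no prior information on the true titre. At CV 10%, σ = 0.0998 and √2·σ = 0.141. For x = 1.9 the probability is 1 − Φ(0.364) = 36%; for x = 1.5 it is 1 − Φ(2.04) = 2%; for x = 0.99 it is 1 − Φ(4.98), effectively zero.

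The table gives four versions for Cohort 3. A and B simulate true titres (A uniform on 0.3-4, B exponential with mean 1.5), with error on both readings and selection on a first reading of 1.0-1.99. C and D average over screening readings uniform on 1.00-1.99; C has error on both readings, D on Day 28 only. Each cell shows the crossing rate, then P(X ≥ 6 of 52).

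| CV | A | B | C | D |
|---|---|---|---|---|
| 5% | 5.6%; 7% | 4.0%; 2% | 5.0%; 4.3% | 3.4%; 0.9% |
| 10% | 11.3%; 54% | 7.9%; 22-23% (simulation error) | 9.9%; 41% | 7.1%; 16% |
| 15% | 16.9%; 89% | 11.9%; 59% | 14.5%; 78% | 10.5%; 47% |

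In Cohorts 1 and 2 the crossing rate stays below 0.01% at all three CVs. The 5% null covers the Cohort 3 rate up to a CV of about 5% with error on both readings, or about 6-7% with error on Day 28 only.

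**Objective 2, same relative rise in everyone, no noise.** With Cohort 3 baselines uniform on 1.00-1.99, a rise by factor m makes (1.99 − 2/m)/0.99 of them responders. For m = 1.25: (1.99 − 1.60)/0.99 = 39%. For m = 1.10: (1.99 − 1.818)/0.99 = 17%. In Cohorts 1 and 2 the share is 0% in both cases. At m = 1.10, Cohort 3 passes its rule with probability 91%, and the Fisher test is significant with probability 99.7%.

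**Effect of a 2-fold condition.** Going from below 1.0 to 2.0 is already more than 2-fold, so Cohorts 1 and 2 are unchanged. In Cohort 3, noise-only conversion falls below 0.1% at CV 15% or less. The condition does not equalise the groups: with Cohort 1-2 baselines uniform on 0.05-0.99, a common 2.5-fold rise still gives 100% in Cohort 3 against (0.99 − 0.80)/0.94 = 20%.

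**The case against.** Reaching an adequate level is a legitimate target. The trial enrols patients without a strong positive response, and section 9.3 frames objective 2 as the likelihood of reaching one. The plan openly expects Cohort 3 to do better. This stands, and it is why the primary definition should not be replaced.

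A reader might infer that Cohort 3 would succeed with an inert booster. The documents do not support that. The null already allows 5% to rise spontaneously, and at a CV of 5% the false-success chance is about 1-7%, around the design value. The inflation depends on an assay CV that is not given. Nor does a 1% rise suffice for Cohort 3 in general; that applies only from about 1.98 upward.

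Section 5.5 says routine testing has already identified many eligible patients, so some may have had two qualifying readings. If all had, the false-success chance at CV 10% under A and B would fall to about 4-11%. Section 5.1 does not require a second reading, so this softens the concern without removing it.

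It is also tempting to make the 2-fold rule primary, as giving both groups the same hurdle. It does not: a patient at 0.5 still needs a 4-fold rise. It also scores 1.95 to 3.8 as a failure and 0.99 to 2.0 as a success. If it lowered the Cohort 3 rate to 30% or 25% (assumed), with 15% in the pooled group, Fisher power would fall from 83% to 63% or 37%.

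**Conclusion.** The point holds as a gap in analysis and wording, not as a flaw in the sample size. It follows from the documents alone that the hurdle is unequal, that one null rate is applied to cohorts with different chances of crossing without a vaccine effect, and that the Fisher test cannot separate distance from the cut-off from responsiveness to the booster. The size is conditional. The 22-89% false-success range assumes a CV of 10-15%, error on both readings, one qualifying titre and the baseline models shown; with error on Day 28 only it is 16-47%. The objective 2 illustration assumes uniform baselines.

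Two wording conflicts need no assumption. Section 9.3 scores a reading of exactly 2.00 both ways, which matters when six responders decide a cohort. And if positive begins at 1.0 S/CO, Cohort 3 cannot seroconvert from negative as the synopsis and section 3 describe.

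**What to change.** - In 9.4.1, pre-specify a sensitivity analysis for Cohort 3 and for objective 2 in which a responder must have a Day-28 titre of at least 2.0 S/CO and at least a 2-fold rise over the pre-booster titre. Attainment of 2.0 S/CO remains the primary definition.
- Report fold rise (Day 28 over baseline) by cohort.
- State that the objective 2 comparison reflects attainment of a level, not relative response, and that the 2-fold condition does not equalise the hurdle.
- Write the cut-off with the same inequality in both sentences of 9.3, carry it into 9.2, and reconcile it with the seroconversion wording in the synopsis, section 3 and section 9.2.

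Both titres are already collected, so the cost is wording and one additional analysis. In that analysis the Cohort 3 rate and the power for objective 2 will be lower, and the plan should say so.
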